**3. METHODS AND PROCEDURES**

**Study Design.** We will perform a 6 weeks, pilot, investigator-initiated, single-center, open-label clinical study to determine the effect of NANODOX® 1% hydrogel in adult AD patients. The study will be conducted in the UF Health Dermatology Department - Springhill.

Subjects that voluntarily agreed to participate will be consented and enrolled in the study. Qualified subjects will be required to come to UF Dermatology Clinic for at least four visits, approximately 2 weeks apart, with an optional pre-screening (up to 28 days +/- 2 prior to V1) visit if washout is needed and/or to allow subjects to be enrolled in pre-established enrollment dates. Each visit will last approximately 30-60 minutes.

Subjects will be asked to apply NanoDOX® Hydrogel 1% once daily at bedtime for total of four weeks (or until complete clearance) on the chosen target eczematous and adjoining clinically normal (perilesional) area (to cover an area of the size of an index card). NanoDOX® Hydrogel 1% will be provided to the patient in single dose package containing 1.5 cc of hydrogel (equal to 15mg Doxycycline) which is enough to cover a skin area of the size of an index card. Alchem will provide drug for the study at no cost. Of note, for systemic use doxycycline is used at concentration from 100 mg (antimicrobial) twice daily to 40 mg (anti-inflammatory) daily for periods ranging from 14 days to several months. We included non-lesional/perilesional skin to evaluate the safety (e.g. irritant or toxic effects) of the compound on atopic skin, as those subjects have a lower irritancy threshold as is compared to non-atopic subjectsxii. Also, skin barrier impairment (e.g. increase water loss & increase pH) can be already detected in normal

appearing skin in AD subjects. It is our hypothesis that by normalizing the proteases activities, treatment with NanoDOX® Hydrogel will normalize skin barrier integrity.

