**Study procedures & methods**

- **Disease status assessment:** **1)** Investigator Global Assessment (IGA), which will provide information of the overall disease (four point scale: clear, mild, moderate, severe) and it is the score requested by FDA for clinical study and **2)** Eczema Area and Severity Index (EASI), a well-accepted and validated scoring system for general disease activityxiv. It is the sum of the intensity scores (0 to 3) for four signs: erythema, induration, excoriation, lichenification and it is recorded for targeted treatment areas as well as four regions of the body (i.e., head, trunk, lower and upper extremities). Data will be reported as percent change in EASI score from baseline and each visit. Proportion of participants achieving EASI50 and EASI75 will be determined at each study timepoints. The presence or absence of skin irritation (e.g. macular/papular eruption), redness, atrophy and telangiectasia will be noted at each study visit.  
**3)** The pruritus intensity will be assessed using the 5-D Pruritus Scale. The pruritus categorical scale is a 4-point scale commonly used in clinical studies of AD and has less of a “middling” effectxv The scale is rated as follows: 0: absence of pruritus; 1: mild, pruritus (occasional slight itching/scratching); 2: moderate pruritus (constant or intermittent itching/scratching that does not disturb sleep) and 3: severe pruritus (bothersome itching/scratching that disturbs sleep).
- **Digital pictures:** A digital picture will be taken with a dedicated digital camera. The pictures will be labeled with the subject’s study ID and date. Pictures will not include identifying information (e.g. facial features, tattoo, etc). Pictures will be taken at a distance for easy identification of the anatomical area and closer to better capture clinical changes. Digital photographs will be used to record the location and monitor the size of target lesions. Quantification of change in size will be obtained using Image J software.  
At conclusion of the study, two trained physicians/dermatologists will be asked to score clinical pictures (0-4 scale, clear, mild, moderate, severe) in a blind fashion (*i.e.*, pictures will be de-identified and presented randomly/ not in chronologic order). This would allow to objectively confirm the clinical score taken during the study.

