## **5. DATA ANALYSIS AND DATA MONITORING**

### **Primary Outcomes:**

1. Assessment of safety and tolerability of NanoDOX® Hydrogel in AD subjects on lesional and non-lesional (clinically normal appearing) skin, including pain and dermatologic/skin toxicity (incidence, severity, frequency, duration and causality) in lesional skin at target site (NanoDOX® Hydrogel). 2. Improvements rate of IGA and EASI score in lesional skin treated with NanoDOX® Hydrogel before and after treatment. We will quantify clinical improvement as: IGA (0-4) fold improvement from baseline; percent of subjects reaching EASI50 (50% improvement over baseline) or EASI75 (75% improvement over baseline) at each time point post treatment (V2 and V4). 3. Objective Clinical improvement based on digital photography scoring (0-4 scale and size of active lesion), measured as fold improvement over baseline at each time point (V2 and V4).

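### Masked reading is specified for the 0-4 photograph score but not for the ImageJ lesion size, so the objective label on primary outcome 3 is unsupported for its size component

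*Combined protocol and SAP*

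**What the plan says.** Section 3 of the combined protocol and SAP describes a "pilot, investigator-initiated, single-center, open-label clinical study". No comparator arm is described.

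Under Primary Outcomes in section 5, the third outcome is "Objective Clinical improvement based on digital photography scoring (0-4 scale and size of active lesion), measured as fold improvement over baseline", assessed at V2 and V4.

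The Digital pictures item under Study procedures & methods deals with the two components separately:

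- **Labelling.** Every picture carries the subject's "study ID and date. Pictures will not include identifying information".
- **Size.** "Digital photographs will be used to record the location and monitor the size of target lesions", and then "Quantification of change in size will be obtained using Image J software". Nothing is said about who does this, when, how the lesion border is set, or whether that person knows the visit.
- **0-4 score.** At the end of the study, "two trained physicians/dermatologists will be asked to score clinical pictures (0-4 scale, clear, mild, moderate, severe) in a blind fashion". The pictures for this reading are de-identified and shown out of date order. Its stated purpose is to confirm the clinical score recorded during the study.

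The analysis text in section 5 applies a Wilcoxon signed-rank test to the blinded evaluation for IGA scores. It names no analysis of lesion size.

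**The concern.** An eczematous patch seldom has a sharp edge. Whether a person outlines it or software finds it by a threshold, somebody chooses where the lesion ends. If that person knows which picture is baseline and expects improvement, small choices can lean the same way in every subject. Without a control arm, such a lean has nothing to cancel against and appears as improvement over baseline.

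The protocol recognises this risk for the 0-4 score and plans a sound remedy. It does not extend the remedy to size, although both sit in the same primary outcome. The visit scores in primary outcome 2 (IGA and EASI) have no masking described either, so the photographs are the clinical efficacy measure for which masking is planned. What is at stake is whether a reported fold improvement in lesion size can be called objective.

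**Working it through.** **1. The plan's own figure.** The only stated power concerns EASI50. With n = 15, a threshold of 6 responses and a true rate of 0.60:

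P(X ≥ 6) = Σ C(15, x) · 0.60^x · 0.40^(15−x), x = 6 to 15, = 0.966.

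This reproduces the stated figure of over 96%. Lesion size does not enter the calculation.

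**2. What is specified for each component of outcome 3.**

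| Item | 0-4 score | Lesion size |
|---|---|---|
| Who measures | two trained physicians or dermatologists | not stated |
| When | end of study | not stated |
| Date and identity removed | yes | not stated |
| Order randomised | yes | not stated |
| Named analysis | Wilcoxon signed-rank, for IGA scores | none |

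The masking provisions appear in the first column only, while section 5 applies the objective label to both.

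**3. How sensitive area is to the border (illustration).** The documents give no lesion diameter and no measurement error. They say only that the treated area, including adjoining normal-looking skin, is about the size of an index card. The inputs below are therefore assumptions: a circular lesion of diameter D that does not change, with the border set e mm outside the true edge at baseline and e mm inside it at follow-up.

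- Apparent fold improvement = ((D + 2e) / (D − 2e))²
- Apparent shrinkage = 1 − ((D − 2e) / (D + 2e))²

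| D (mm) | e (mm) | Fold improvement | Apparent shrinkage |
|---|---|---|---|
| 50 | 1 | (52/48)² = 1.17 | 14.8% |
| 50 | 2 | (54/46)² = 1.38 | 27.4% |
| 100 | 1 | (102/98)² = 1.08 | 7.7% |
| 100 | 2 | (104/96)² = 1.17 | 14.8% |

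Doubling the diameter roughly halves the effect. The calculation takes the errors to run in opposite directions at the two visits. Border errors unrelated to visit would add noise without a systematic shift. The table shows how much a small directional choice can do; it does not estimate the bias in this trial.

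**The case against.** A reader might infer that size is hand-traced by an unblinded operator. The documents do not support that. They say ImageJ will be used and are otherwise silent on operator, method and masking. The date label does not settle it either: the same pictures carry it before they are de-identified for the two readers, so it can be removed. The wording of outcome 3 also places size inside photographic scoring, and one could read it as part of the masked exercise. The procedure text does not confirm this, because it limits that exercise to the 0-4 scale and to confirming the clinical score. What stands is that masking of size is unspecified.

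A reader might also infer that the photographs are the trial's only protection against biased efficacy readings. They are not. Section 5 lists bacterial culture and instrument-measured barrier function as secondary outcomes, and the blinded 0-4 score is untouched. Nor can size be called half of outcome 3, since the plan gives its components no weights.

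Finally, this is a 15-subject proof of concept, and no test or threshold uses lesion size. That limits the consequence, but it does not justify leaving a named component of a primary outcome less protected than its partner when the masked pictures are already required. Masking may be imperfect where an optional biopsy of the treated site at V3 leaves a visible mark at V4. That limitation applies equally to the 0-4 score.

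**Conclusion.** The point holds as a gap in specification with a cheap remedy. The plan provides masked reading for one component of outcome 3 and none for the other, in an open-label study with no control arm described. Size may therefore be measured with knowledge of the visit, and calling it objective is not supported by the text.

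The possible size of the effect, about 8-27% apparent shrinkage, rests wholly on the assumed circular shape, diameters of 50-100 mm and opposite border shifts of 1-2 mm. The consequence is confined to outcome 3. The EASI50 criterion, its power of 0.966 and the blinded 0-4 reading are unaffected, and nothing here calls the trial as a whole into question.

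**What to change.** Amend the Digital pictures item under Study procedures & methods to say that ImageJ size will be measured at study end on the same de-identified, randomly ordered pictures used for the 0-4 score, with date and visit masked until all areas are locked. A sentence stating how the lesion border is set would help the measurer apply one standard throughout, but masking is the essential change.

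The masked picture set must be prepared in any case. The cost is the amended wording, a little extra handling and measuring work, and the loss of size results before study end. Sample size, visits and the EASI50 rule stay as they are.

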**Visit 2 (Day 14 +/-2):**

- 1) Review subject diary and address any questions, concerns, or missed doses
- 2) Questionnaire to clinically characterize AD, review of medications and possible SE
- 2) Clinical score for atopic dermatitis
- 3) Digital pictures of the targeted area
- 4) Non-invasive skin barrier Measurements: transepidermal water loss. Optional: pH and SC hydration measurements may also be performed.
- 5) Repeated tape strippings (0, 5, 10, 15 tape-strippings with Cuderm™ tape)
- 6) Dispense NANODOX® for two following weeks (14 +/-2 monodose packages)
- 7) Suture removal at pre-treatment biopsy site, if applicable
- 8) Review Diary instructions
- 9) Provide date of Visit 3 and “morning of appointment” instructions

In case of complete resolution of the treated area at V2, post treatment biopsy and swab and Venous blood draw will be performed at this visit (instead V3) and patient will only come back for 2 weeks post treatment.

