**Visit 3 (Day 28 +/-2):**

- 1) Review subject diary and address any questions, concerns, or missed doses
- 2) Questionnaire to clinically characterize AD, review of medications and possible SE
- 3) Clinical score for atopic dermatitis
- 4) Digital pictures of the targeted area
- 5) Non-invasive skin barrier Measurements: transepidermal water loss. pH and SC hydration measurements may also be performed.
- 6) Repeated tape strippings (0, 5, 10, 15 tape-strippings with Cuderm™ tape)
- 7) Skin swab of treatment area
- 8) Optional skin biopsy (5 mm punch) from treatment site and non-treatment site if not performed at Day 1 visit.
- 9) Venous blood draw
- 10) Provide date of Visit 4 and “morning of appointment” instructions

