**Visit 4 (Day 42 +/-5):**

- 1) Questionnaire to clinically characterize AD, review of medications and possible SE
- 2) Clinical score for atopic dermatitis
- 3) Take digital pictures of the targeted area
- 4) Non-invasive skin barrier Measurements: transepidermal water loss. pH and SC hydration measurements may also be performed.
- 5) Repeated tape strippings (0, 5, 10,15 tape-strippings with Cuderm™ tape)
- 6) Suture removal at biopsy site(s)

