- **Skin swab:** Skin swabs will be collected for microbiologic analysis to obtain a semi-quantification of skin bacteria pool, including *S. aureus* spp. and to determine antibiotic sensitivity. Skin swabs are performed by swiping and rolling a sterile cotton-tipped applicator 4-5 times across the target area. Swabs will be obtained from NanoDOX® Hydrogel sites pre and post treatment and may be repeated as needed to monitor

bacteria growth during study. The microbiology assay will be run by the Clinical microbiology laboratory at the University of Florida (Rocky Point Lab).

- **Optional Skin biopsy:** One skin biopsy sample (5 mm  $\approx$  pencil eraser size) will be obtained if possible within 4 cm from the treatment area or on the contralateral side. Second biopsy will be obtained from the treatment area post-treatment. Biopsy will be performed after injecting a local anesthetic (Lidocaine +/- epinephrine) to minimize pain and bleeding. The biopsy will consist of removing a piece of skin with a sterile 5-mm skin biopsy punch. At the biopsy site one or two sutures will be placed to ensure better healing, minimize blood loss and to provide a more aesthetic scar formation. A pressure bandage will be applied to the biopsy site to minimize the risk of bleeding and infection. We will provide each subject with a wound care instruction sheet.

Each biopsy will be used for analysis of proinflammatory cytokines (TSLP, IL33, TNF $\alpha$ , IL-1b, and IL-6) and epidermal barrier related protein (e.g. filaggrin, loricrin, claudin1, S100A7) as well as proteases activity (MMPs, elastase) that are typically upregulated in inflammatory skin. This will be done in collaboration with [name] (Professor of Obstetrics/Gynecology & Ophthalmology at the University of Florida, co-PI in the study). It is our hypothesis that NanoDOX $\text{\textcircled{R}}$  Hydrogel by reducing the proteases activity in the epidermis will enhance the integrity of epidermal barrier structure. Secondly, we will evaluate changes in inflammatory (and pro-inflammatory) pathways downstream to proteases activity before and after treatment with NanoDOX $\text{\textcircled{R}}$  Hydrogel. We expect that normalization of molecular pattern parallels clinical improvement (and restore of skin barrier integrity).

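### In subjects biopsied in the target area, a visible wound or scar marks the V4 photograph as post-treatment, so shuffling does not blind the baseline-versus-V4 photograph reading

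*Combined protocol and SAP*

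**What the plan says.** All references are to the combined protocol and SAP.

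- **Biopsy site.** Study procedures & methods, Optional Skin biopsy: "Second biopsy will be obtained from the treatment area post-treatment". The same entry adds: "At the biopsy site one or two sutures will be placed to ensure better healing".
- **Biopsy timing.** Visit 3, item 8: "Optional skin biopsy (5 mm punch) from treatment site and non-treatment site if not performed at Day 1 visit". For early clearers the Visit 2 section brings it forward: "In case of complete resolution of the treated area at V2, post treatment biopsy".
- **Visit 4 order.** The clinical score is item 2 and the photograph item 3 ("Take digital pictures of the targeted area"). Removal of biopsy sutures is item 6.
- **Lasting mark.** Risks of Punch Biopsy puts suture removal at 14 (+/- 2) days and says a small scar will remain, possibly with altered pigment.
- **Blinding.** Study procedures & methods, Digital pictures: two physicians score the pictures at the end of the study, and "pictures will be de-identified and presented randomly/ not in chronologic order". Masking, cropping or exclusion of the biopsy site is not mentioned.
- **Use.** Primary Outcomes, item 3, compares photograph score and lesion size with baseline at V2 and V4. The analysis text under Secondary Outcomes applies a Wilcoxon signed-rank test to the blinded pre-versus-post evaluation without naming the post visit.

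**The concern.** The study is open-label with a single arm. The photograph reading is the only efficacy measure for which the protocol describes blinded assessment, and its stated role is to confirm the unblinded clinical score objectively. Blinding here means that a reader cannot tell a baseline picture from a later one. A sutured punch wound or fresh scar inside the target tells the reader exactly that, whatever order the pictures come in. A reader who expects improvement could then score the recognised picture more favourably, and the confirmation would share the bias it is meant to exclude. The plan uses the V4 picture, which can carry the mark, and does not list the V3 picture, which is taken before the V3 biopsy.

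**Working it through.** **1. The plan's own figure.** With X ~ Binomial(15, 0.60), P(X ≥ 6) = Σ C(15,x)·0.6^x·0.4^(15−x) for x = 6 to 15, which is 0.966. This agrees with the stated power of over 96%. The rule counts EASI responses, and photographs do not enter it.

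**2. Order of procedures, from the visit lists.**

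| Visit | Photograph | Biopsy | Suture removal |
|---|---|---|---|
| V1, Day 0 | item 7 | item 11, comparator, outside the treated area, optional | none |
| V2, Day 14 ± 2 | item 3 | target biopsy in early clearers; place in the list not given | item 7, comparator site |
| V3, Day 28 ± 2 | item 4 | item 8, target (and comparator if deferred) | none |
| V4, Day 42 ± 5 | item 3 | none | item 6 |

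V1 and V3 photographs are listed before any punch in the target. The V4 photograph follows it.

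**3. What V4 can show.** V3 to V4 is nominally 42 − 28 = 14 days. The windows allow 37 − 30 = 7 to 47 − 26 = 21 days, while sutures are due out 12 to 16 days after biopsy. As listed, the V4 picture is taken with sutures in place. If they have come out earlier, a recent scar remains.

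**4. Size of the mark.** Punch area is π × 0.25² = 0.196 cm². The protocol describes the treated area as the size of an index card. Assuming 7.62 × 12.7 cm = 96.8 cm², the punch covers 0.196 / 96.8 = 0.2%. That is small for scoring but does not prevent recognition.

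**5. Illustration of the reader effect (all inputs assumed).** No true change; 15 subjects; underlying grades 1, 2 and 3 with probabilities 0.2, 0.5 and 0.3; reading error of one grade with 20% chance each way; two-sided 0.05 signed-rank test; 4,000 simulated trials per setting. Readers lower a recognised V4 score by one grade in 25% to 50% of cases.

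| Subjects with a recognised V4 picture | Trials falsely showing improvement |
|---|---|
| 0 | about 2% |
| 5 | 3% to 7% |
| 10 | 7% to 18% |
| 15 | 13% to 39% |

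The direction follows from the assumption that readers favour later pictures. The size depends on inputs the documents do not give.

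**6. The opposite effect on the live score.** Erythema and induration are two of the four EASI signs, and EASI is also recorded on the target. Wound redness could therefore raise the V4 score and hide benefit. If, by assumption, 5%, 10% or 20% of true responders were lost this way, the response rate would fall from 0.60 to 0.57, 0.54 or 0.48, and P(X ≥ 6) to 94.4%, 91.1% or 81.0%. Nothing in the documents shows that any are lost, and a response can also be met at V2.

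**The case against.** **The biopsy is optional and uptake is unknown.** This stands. The affected number may be zero, and it bounds the claim.

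**Not every biopsied subject need be marked.** This also stands. The treated area includes adjoining normal skin, the protocol does not say the punch is lesional, and a subject may give only the comparator biopsy. The point holds where the mark is visible.

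**A reader might infer that the whole picture sequence is revealed.** The documents do not support that. A wound in the target identifies V4 only; the other pictures remain shuffled. Identifying V4 is still enough to unblind baseline versus V4.

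**A reader might infer that V2 blinding is generally lost as well.** It is not. The comparator biopsy must avoid the treated area, may be on the opposite side, and may be deferred to Day 28. A V2 cue needs a same-side Day-0 biopsy visible in the frame ("Suture removal at pre-treatment biopsy site, if applicable" is listed after the V2 picture), or an early clearer biopsied before the V2 picture is taken.

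**A reader might infer that V4 barrier data are compromised.** The listed barrier outcome runs from V1 to V3, and V3 TEWL is listed before the V3 biopsy. V4 TEWL lies outside it.

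**The live scorer can tell a punch from eczema.** That is fair, and any EASI effect is unquantified. It would tend to hide benefit, whereas reader unblinding would tend to exaggerate it, so the two cannot be assumed to cancel.

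**Conclusion.** The point holds for the V4 photograph of subjects biopsied in the target area, 0 to 15 of 15. Where the wound or scar shows, de-identification and random order do not blind the baseline-versus-V4 comparison in primary outcome 3. If V4 is the post visit in the Wilcoxon test, that test is affected too. This rests on the listed order of procedures and on the absence of any masking step. The simulated error rates only illustrate what recognition could do. V2 is affected in limited cases. Effects on V4 target EASI and traced lesion size are possible but unquantified. The 6-of-15 rule does not use the photographs, so this finding does not overturn it.

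**What to change.** 1. In the Digital pictures entry, require that before the blinded reading someone other than the readers crops each subject's pictures to the target area. That person then places one identical opaque mask over the biopsy location on all of that subject's pictures, including V1. The mask must cover wound, sutures and surrounding redness.
2. Exclude the same patch from lesion-size tracing at every visit.
3. Have the pre-biopsy V3 picture read as the wound-free end-of-treatment comparison. For early clearers, take the V2 picture before the biopsy. Name the post visit for the Wilcoxon test.
4. Report photograph results and V4 target-area EASI by biopsy status. Do not drop the patch from EASI at V4 alone: baseline EASI includes it, and if the punch removed residual lesion the comparison would favour improvement.
5. Reconcile the 7-to-21-day interval that the visit windows allow between V3 and V4 with the 12-to-16-day suture-removal window.

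The cost is a few minutes of image preparation per subject, one extra picture per subject to read, and some lesion left unscored. A mask 1 to 2 cm across covers π × 0.5² = 0.785 to π × 1² = 3.14 cm². On an assumed lesion of 10 to 40 cm² the loss runs from 0.785 / 40 = 2% to 3.14 / 10 = 31%. Masking can be done at any time before the end-of-study reading, and no biopsy procedure changes.
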